- 18. In selecting L-DOPA doses, we balanced appropriate safety concerns regarding the use of this medication in a novel patient population with the goal of causing a measurable effect. L-DOPA is an extremely well tolerated medication at doses < 600mg, which is substantially less than the doses often reached in the treatment of Parkinson's disease (900-1200mg). L-DOPA has been administered to healthy subjects in single dose studies and found to be well-tolerated. In Parkinson's disease, a recent clinical trial published in the New England Journal of Medicine randomized patients to receive 150mg, 300mg, or 600mg L-DOPA for 40 weeks. In the 150mg and 300mg L-DOPA treatment groups, the only side effects

observed that were different from placebo were headache and nausea. No dyskinesias or other neuropsychiatric effects were observed that were greater than the placebo group. In terms of effects, single-dose studies have reported significant effects on cognition and neural activation with L-DOPA doses as low as 100mg. Thus, we believe the 150-450mg dose range to be used in this study will be both safe and likely to produce an observable effect.

Assessments

- 19. Subjects are expected to have a screening/evaluation visit, PET/MRI scanning day (for those receiving imaging), and weekly visits from Week 0-3.
- 20. At baseline, we will record each subject's chief complaint, referral source, age of onset of mood and/or cognitive decline, number prior depressive episodes, age, sex, marital status, race and ethnicity, years of education, employment status and income, years of education, family history. We also will document medical history, physical exam, urine drug screen, CBC, chemistries and electrolytes, thyroid profile, vitamin B12 and folate levels, urine analysis, and ECG. Vital signs will be measured at baseline and monitored weekly throughout the study. The Cumulative Illness Rating Scale-Geriatric (CIRS-G) (112) will be filled out at baseline to measure chronic medical illness burden. Subjects' current physical pain will be assessed weekly using a 100mm Pain Visual Analog Scale (VAS) and used as a covariate in analyses of gait speed (113).
- 21. The following measures will be collected weekly throughout the study: 24-item HRSD, CGI Severity and Improvement, Structured Pill Count Interview, Unified Parkinson's Disease Rating Scale (UPDRS) (questions 32 and 33 will be used in this study to assess the duration and disability of dyskinesias caused by L-DOPA), Treatment Emergent Side Effect Scale, and Inventory of Depressive Symptoms—Self Report (IDS-SR).
- 22. In addition, processing and gait speed assessments will be performed weekly at 1pm to control for time of day effects and the duration since the last morning L-DOPA dose (anticipated to be 4 hours). Processing speed will be assessed using the Digit Symbol test from the Wechsler Adult Intelligence Scale-III (WAIS-III) (119) and the Pattern and Letter Comparison tests (120). These tests are all reliable and valid, with moderate to high loadings on the latent speed factor. A latent factor (and subsequent factor score) will be extracted from the 3-test battery pre- and post-treatment and used as the main outcome in the R61. By extracting a latent factor and factor loadings we will utilize a more pure measure of processing speed than if we used the raw scores from an individual test or a sum total score from the three raw scores combined (121-124).
- 23. Gait will be assessed as both a single and dual task (ST, DT) on a 15' walking course in the LLDC. For the ST, patients are instructed to walk at their usual or normal speed over the 15' walking course. For the DT, patients are instructed to walk at their usual pace while simultaneously verbally listing as many animals as possible (fluency DT). In addition, a counting DT will be used in which patients are instructed to walk at their usual pace while simultaneously performing serial subtractions by threes starting at 100 (125). Patients will start and end at a point 2 meters from beginning of the 15' course to eliminate acceleration and deceleration effects. Each ST and DT will be assessed two times with the average used in the analyses. The ST assessment of walking speed in m/s will be used as the primary outcome measure for this study.

End of study procedures

24. Following the 3 week duration treatment study, endpoint assessments will be made. Patients will enter 3 month open treatment period provided free of charge as described below.

You can upload charts or diagrams if any

Criteria for Early Discontinuation

Criteria for Early Discontinuation

The risk of non-response or adverse events to L-DOPA during the study period is addressed by having close clinical follow up of study subjects and stringent withdrawal criteria. These criteria are (1) participant withdraws his or her consent; (2) significant clinical worsening as defined by a slowing assessment rating using the CGI-Improvement scale of 6 (worse) or 7 (much worse) for 2 consecutive visits; or (3) development of significant side effects or an adverse event. Any subjects meeting any of these criteria will be withdrawn from the study and treated clinically. Furthermore, subjects may be withdrawn if they repeatedly miss scheduled appointments or clinical worsening necessitates more intensive treatment. No treatment is currently available for slowing, so there is not a standard of care treatment to offer patients withdrawn from the study. Thus, withdrawn patients will be followed in the open treatment period, offered appropriate psychiatric treatments if they have any conditions requiring treatment (e.g., depression), and be referred to their internist for close medical follow up.

Blood and other Biological Samples

Please create or insert a table describing the proposed collection of blood or other biological specimens A 20cc blood sample will be drawn at baseline. General medical tests will be performed, such as CBC, Chem 7, LFTs, TSH, cholesterol, B12, and folate.

Assessment Instruments

Create a table or give a brief description of the instruments that will be used for assessment

Structured Clinical Interview Diagnostic for DSM 5 (SCID) (114): this semi-structured diagnostic interview will allow determination of whether subjects meet selection criteria.

Center for Epidemiologic Studies—Depression Scale (CES-D): depression screening measure chosen given its ease of administration and wide use in epidemiological studies.

MMSE: standard means of assessing global cognition. The SCID, CES-D, and MMSE will be measured at baseline for the purpose of subject selection, while the following measures will be collected weekly throughout the study.

24-item HRSD (115): standard measure of depression severity that measures changes in depressive symptoms, though L-DOPA effects on depression are not the focus of the R61 Phase.

CGI Severity and Improvement: scales measuring the clinician's view of subjects' global functioning that will provide a clinical assessment of subjects at each visit and help maintain safety by identifying clinical worsening.

Structured Pill Count Interview: assessment of study medication compliance accounting for each dose of prescribed study medication during the study period.

Unified Parkinson's Disease Rating Scale (UPDRS) (116): standardized, reliable, and valid instrument for assessing the severity of the clinical features of PD; questions 32 and 33 will be used in this study to assess the duration and disability of dyskinesias caused by L-DOPA. While we include this measure, we are not expecting to observe dyskinesias in healthy subjects or at the L-DOPA doses being used in this study. Typically, such L-DOPA side effects emerge only in patients who have had Parkinson's disease for a number of years and then only if the LDOPA dose is raised to 600 mg or more.

Treatment Emergent Side Effect Scale: standardized general checklist used in our clinic for monitoring side effects associated with medication treatment

Inventory of Depressive Symptoms—Self Report (IDS-SR) (117): rating scale for depressive symptoms based on DSM criteria that has been increasingly used in antidepressant studies due to its equivalent weightings for each item, understandable anchor points, and inclusion of all DSM criteria (118).

Please attach copies, unless standard instruments are used

Off label and investigational use of drugs/devices

Choose from the following that will be applicable to your study

✓ Drug

✓ Radiolabeled drug/compound

Select the number of drugs used in this study

Drug #1

Name of the drug carbidopa-levodopa

Manufacturer and other information

We will be using generic sinemet 25/100 tablets in this study. We will purchase them through the pharmacy, using whichever generic manufacturer is recommended by the NYSPI pharmacy.

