- 6. Half of the total sample will undergo neuroimaging (N=30 of total N=60). Subjects will undergo a pretreatment MRI and PET scan and a post-treatment MRI and PET scan (i.e., 2 total MRIs, 2 total PET scans, separated by the 3 week clinical trial). Subjects who do not meet imaging selection criteria or who do not wish to undergo scanning will be allowed to participate in the clinical trial portion of the study only. MRI and PET scanning may occur on the same day if this can be scheduled (MRI occurring first, followed by PET scan). However, due to the tightness of scheduling for these scanners, it is more likely that the MRI and PET scans will occur on different days--one day for MRI scan and one day for the PET scan. Typically the MRI scanning day will come before the PET scanning day.
- 7. MRI of the brain will be acquired using a GE MR750 3.0T System. At the start of the session, a 3-Plane localizer (scout) will be acquired to determine patient position. Subjects will then receive T1-weighted 3D SPGR (Spoiled Gradient Echo), T2 FLAIR, and EPI scans. Acquisition parameters for the EPI scans will be: TE/TR (ms) 20/2000; Flip Angle (deg) 720; in-plane resolution (voxels) 112x112; slice thickness/gap (mm) 3/0; slices 41.

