- 13. Post-treatment scan: As close to the end of the 3 week study as possible (based on PET scheduling), subjects will undergo their post treatment scan. We will follow standard procedures for measuring L-DOPA-induced changes in synaptic dopamine levels set forth in PET studies of PD patients. Subjects will be given 75mg carbidopa/300mg L-DOPA approximately 1.5 hours before scanning. Subjects in week 3 of the protocol are taking 450mg LDOPA per day (150mg three times daily), so the 300mg administered prior to the post-treatment PET scan will constitute 300mg of their usual 450mg daily dose on the scan day. A low dose CT transmission scan is obtained prior to intravenous administration of 14mCi [11C] raclopride (or less). The start of tracer injection will be timed to coincide with the time of onset of L-DOPA effects (approximately 60-90 minutes following oral dose). Thus, the 60 minute PET scanning session will occur from 90 minutes to 150 minutes following L-DOPA dosing in all subjects. At the completion of the scan the IV catheter will be removed, and the subject will be evaluated (including mental status and vital signs) by a study physician. Vital signs, and physical exam will be performed prior to discharge from the PET suite.
- 14. We are aware that the scanning dose of 300mg given at once approximates but may not match the CNS effects of subchronic dosing with 150mg tid. However, this method has the advantages of being consistent with imaging studies of PD patients in which L-DOPA doses are typically 250-300mg and avoiding confounding of Δ BPND estimates by downregulation of D2 receptors occurring with subchronic administration. Since nausea is a known side effect of L-DOPA, we will be particularly vigilant about monitoring for it. When nausea occurs patients generally feel warm and sick to their stomachs. It will likely

occur after PET scanning, but if vomiting were necessary, the MD would remove the subject from the scanner so that vomiting does not occur while supine. Removal from the scanner can occur immediately.

- 15. PET data will be reconstructed into images using the appropriate reconstruction protocols and filters. PET images will be coregistered to the MRI and regional time activity curves will be measured. Data will be fitted to pharmacokinetic models, and relevant pharmacokinetic parameters, including the percent of receptors engaged by dopamine, will be estimated based on the model fitting procedures.

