- 16. Drs. [name] and [name] continue to be Co-Investigators responsible for neuroimaging as part of a subcontract executed between RFMH and SUNY-Stony Brook. They will lead analyses of neuroimaging data. In terms of on-site execution of PET and MRI scans, these are supervised by the study PI ([name]) and/or [name], who works with the Aging Program as a study clinician and has a research background in PET neuroimaging.

Clinical treatment

- 16. An effort will be made for all subjects to be titrated up to 450mg L-DOPA over a 3 week-duration study. We chose 450mg as the target dose because it is higher than doses known to affect cognition (i.e., 150-300mg) but lower than levels used for PD (i.e., 600-1200mg) that may have greater side effects. Each subject will start taking 37.5mg carbidopa/150 mg levodopa (1.5 25/100 sinemet tablets) once daily for one week, then increase to 75mg carbidopa/300mg levodopa (1.5 25/100 sinemet tablets twice daily) for one week, and finally increase to 112.5mg carbidopa/450mg levodopa (1.5 25/100 sinemet tablets three times daily) for one week. Each subject will be titrated to 450mg L-DOPA unless they cannot tolerate higher doses, in which case subjects will have their dosage reduced to the maximum tolerable dose.
- 17. Although each subject is titrated up to 450mg L-DOPA if it is tolerated, the study design allows us to assess the effects and tolerability of three different L-DOPA doses (150mg, 300mg, and 450mg). Based on published work using L-DOPA for PD, we expect effects on cognition and gait to be apparent at each dosing level approximately 5 days after dosage increases. By performing assessments weekly, we will thus obtain measures of L-DOPA's effect on processing and gait speed at each dosing level. We carefully reviewed the literature and consulted our Co-Investigator [name] (neurologist and PD expert) for evidence of carry-over effects of L-DOPA dosing (such that prior experience with 150mg and 300mg may influence a subject's experience of receiving 450mg). We found little evidence to suggest there are significant carry-over effects from previous L-DOPA doses, so each dose will be able to be assessed on its own merits. Similarly, we do not anticipate that the repeated assessments of processing and gait speeds will bias the study results.

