2. L-DOPA Side Effects: Side effects will be assessed at each planned visit and if needed through additional or unscheduled contacts. We will attempt to minimize side effects by slow dosage titration and allowance for dose reduction if needed. We will withdraw subjects from the study if they cannot tolerate the lowest dose of carbidopa/levodopa (L-DOPA) 37.5mg/150mg daily.

L-DOPA is a well-tolerated medication at the doses we will be using in this study. Older (i.e., 1960s-70s era) case studies report administering L-DOPA doses of 400-1200mg and in some cases much higher to depressed, non-PD patients over subacute time periods (4-12 weeks). Variable clinical results were observed, but few side effects were reported and no dyskinesias. More recently, a double-blind study (conducted by Co-Investigator [name] and colleagues) of a single dose of L-DOPA 200mg vs. placebo investigated the role of dopamine in the impaired interval timing abilities observed in older adults. Thirty two healthy aged participants aged 71.2 ± 7.6 years were trained to produce two target time intervals (6 and 17 seconds in duration) in separate blocks corresponding to drug/placebo administration. Of the 16 elderly subjects who took 200mg L-DOPA, no severe side effects were noted, and no individuals discontinued participation in the study. Forty-four percent reported mild nausea at some point during the experiment, which was the only side effect noted. There are sporadic other reports in the literature examining the effects of single-dose 200mg L-DOPA on cognitive outcomes in healthy controls (e.g., Rihet et al, Psychopharmacology 2002; Hasbroucq et al, Psychopharmacology 2003), but no other recent (i.e., post 2000) studies have been performed of subacute L-DOPA dosing in healthy controls.

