- 2. Side effects will be assessed at each planned visit and if needed through additional or unscheduled contacts. We will attempt to minimize side effects by slow dosage titration and allowance for dose reduction if needed. We will withdraw subjects from the study if they cannot tolerate the lowest dose of carbidopa/levodopa (L-DOPA) 37.5mg/150mg daily.

- 3. The dose of radiation will be submitted for approval to the JRSC. All scans will be done in the presence of medical supervision and trained nursing staff in an imaging center specifically designed to support imaging studies. In the event of serious medical complications, the PET scan facilities have immediate access to a consultation with specialized medical units at New York Presbyterian Hospital. Preparation of radiopharmaceuticals and performance of PET scans will be by radiochemists, physicians, and technologists of the Department of Radiology at Columbia. These professionals are qualified by training and experience in the safe use and handling of radiopharmaceuticals. Subjects will be asked about their previous radiation exposure and those who have had research exposure within the past year will be excluded if their cumulative annual exposure (including the present study) exceeds FDA limits. The information on the previous radiation exposure of study subjects will be notified to the study doctor.
- 4. In terms of raclopride pharmacologic effects, we do not anticipate any pharmacological effects from the radiotracer used in the proposed studies. As with any drug, the possibility of idiosyncratic reaction exists and is mentioned in the consent forms. A physician is present at each experiment.
- 5. To minimize MRI risks, each subject will fill out the MRI Safety Questionnaire before the study. Only subjects who fulfill the criteria by this questionnaire will be eligible for the study. In addition, subjects will remove all metal (watch, hair pins, jewelry) before entering the MRI room. If the subject has any metallic prostheses/implants they will be excluded from the study. If a subject becomes anxious during the scan they can request that the MRI scan be stopped.

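### The fixed 300 mg scan-day dose assumes a 450 mg/day background and is not made conditional on tolerability, although the protocol keeps subjects who tolerate as little as 150 mg/day

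*Combined protocol and SAP*

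**What the plan says.** The scan-day dose is set in PET Scanning, item 13: "Subjects will be given 75mg carbidopa/300mg L-DOPA approximately 1.5 hours before scanning". The sentence carries no condition on the dose the subject is then taking. The justification is that subjects in week 3 are on 450 mg/day in three doses, so that "the 300mg administered prior to the post-treatment PET scan will constitute 300mg of their usual 450mg daily dose on the scan day". Item 14 confirms that the 300 mg is a single administration.

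Clinical treatment, item 16, sets the titration. Subjects start on 150 mg once daily, "then increase to 75mg carbidopa/300mg levodopa (1.5 25/100 sinemet tablets twice daily) for one week", and reach 450 mg/day in the third week. They go up "unless they cannot tolerate higher doses, in which case subjects will have their dosage reduced to the maximum tolerable dose". Item 2 of the Risks section gives the floor: "We will withdraw subjects from the study if they cannot tolerate the lowest dose of carbidopa/levodopa (L-DOPA) 37.5mg/150mg daily". Item 2 of the procedures for minimizing risks repeats that floor and adds: "We will attempt to minimize side effects by slow dosage titration and allowance for dose reduction if needed".

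Two further provisions bear on who reaches the scan. MRI Scanning, item 6, lets some people take part in the clinical trial only: "Subjects who do not meet imaging selection criteria or who do not wish to undergo scanning". The Criteria for Early Discontinuation include "development of significant side effects or an adverse event". The exclusions that apply only to PET subjects are MRI contraindication or inability to tolerate scanning, and past radioactivity exposure.

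**The concern.** Item 13 and item 16 describe different week-3 populations. Item 13 treats everyone as being on 450 mg/day. Item 16 and the risk sections expect that some will not be, and keep them in the study at a lower dose. For those subjects the premise of item 13 is false, and the dose it supports may exceed everything they have been shown to tolerate in a day.

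This is a safety matter first. The dose-reduction rule protects subjects who react badly to the drug, and the scan procedure, followed literally, sets that protection aside on one day for the same subjects.

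**Working it through.** The plan states no sample-size or error-rate figure on this point, so there is none to reproduce. The check is dose arithmetic followed by a reading of the rules side by side.

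**Tablet arithmetic** (25/100 tablets, Clinical treatment item 16):
- 1.5 tablets once daily = 37.5/150 mg
- 1.5 tablets twice daily = 75/300 mg
- 1.5 tablets three times daily = 112.5/450 mg
- Scan dose of 75/300 mg = 3 tablets at once

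The protocol's stated doses are correct.

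**Scan dose relative to background** (300 mg divided by the daily dose, and by the usual single dose of 150 mg):

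| Daily dose | Scan dose / daily dose | Scan dose / usual single dose |
|---|---|---|
| 450 mg | 300/450 = 0.67 | 300/150 = 2.0 |
| 300 mg | 300/300 = 1.0 | 300/150 = 2.0 |
| 150 mg | 300/150 = 2.0 | 300/150 = 2.0 |

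Doubling the usual single dose is common to all three scheduled levels and is part of the design. What sets the low-dose subject apart is the middle column: above 1.0, the challenge exceeds the whole tolerated daily amount. This is also true between the steps. If a subject were held at 200 or 250 mg/day, the ratios would be 300/200 = 1.5 and 300/250 = 1.2.

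**Reading the rules together:**
1. A subject held below 300 mg/day for intolerance has, by the meaning of a maximum tolerable dose, not tolerated 300 mg/day.
2. Item 16 delivers 300 mg/day as two doses of 150 mg.
3. The subject stays in the study as long as 150 mg/day is tolerated.
4. Neither the PET-only exclusions nor MRI Scanning item 6 mentions tolerated L-DOPA dose, so a willing subject who passes imaging screening remains due for the scan.
5. Item 13 then gives 300 mg in one administration.

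**How many could be affected.** The documents do not say what share of subjects was held below 300 mg/day. As an assumption, let that share be p among the 30 planned imaged subjects. The expected number is 30p, and the chance of at least one is 1 − (1 − p)^30:

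| p | Expected number | Chance of at least one |
|---|---|---|
| 2% | 0.6 | 0.455 |
| 5% | 1.5 | 0.785 |
| 10% | 3.0 | 0.958 |
| 20% | 6.0 | 0.999 |

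These figures show sensitivity to p. They are not estimates for this trial.

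**The case against.** The best reply is that item 13 describes the standard case and was never meant to override the tolerability rules. Its reference to all subjects governs scan timing, not dose. The risk sections allow dose reduction, and also promise to assess new complaints for a possible change in study drug dosing. Significant side effects lead to withdrawal, subjects may decline scanning or leave, and item 14 plans nausea monitoring with immediate removal from the scanner. The one tolerability figure for a single dose is also reassuring: mild nausea in 44% of 16 healthy older adults after 200 mg, with nothing severe and no discontinuations.

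Much of this stands. A reader might infer that nothing in the plan could have stopped the dose. That is too strong: clinicians had general discretion before the scan, and subjects could refuse. What remains is that none of these provisions refers to the scan dose. Item 14 treats that dose as a deliberate departure from regular dosing, so it cannot be assumed that the titration rule governs it. Withdrawal does not close the gap either, because the subjects concerned are those who were reduced and kept. The 44% comes from people not selected for intolerance and says little about them.

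Two other inferences are unsupported. A reader might suspect bias in Aim 1, but every scan under item 13 uses the same 300 mg challenge that Hypothesis 1 names, and no data by background dose are given. A reader might also see a gap for scans falling after Week 3. Item 9 places the scan at the end of the trial, and no text says that one fell later.

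**Conclusion.** The inconsistency is real and minor. The stated basis for the scan dose is false for any subject kept below 450 mg/day. For a subject kept below 300 mg/day, the written procedure conflicts with the protocol's own tolerability rule, giving up to 2.0 times the tolerated daily amount at once. The conclusion assumes that such a subject was reduced because of intolerance and was still due for the scan. The fixed challenge for subjects on 300 or 450 mg/day is not in question.

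Two facts limit the weight. The number affected is not reported and may be zero. The continuation application also states that all research interventions are complete, so new wording cannot change any dose already given. A reader might infer that someone was harmed; nothing in the documents says so.

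**What to change.** Replace the sentence in item 13 about the usual 450 mg with a rule:
- Only subjects whose maximum tolerable dose is at least 300 mg/day receive the fixed 300 mg challenge and the post-treatment PET scan.
- Any subject held below 300 mg/day, including at an intermediate dose, does not receive it, stays in the clinical part, and is recorded as not scanned for tolerability.

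Omitting the scan is preferable to capping the dose, because a capped dose would no longer test the 300 mg in Hypothesis 1.

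The prospective cost is possibly a few scans, with Aim 1 then applying to subjects who tolerate at least 300 mg/day. As an assumption, take a loss of 1 to 3 scans with the spread of binding changes unaltered. From the planned 30, the standard error grows by a factor of √(30/29) = 1.017 to √(30/27) = 1.054, that is 1.7% to 5.4%. The reported 24 degrees of freedom for the binding-change tests imply 25 scan pairs; from 25 the factors are √(25/24) = 1.021 to √(25/22) = 1.066.

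For the completed study, list each imaged subject's daily L-DOPA dose at the time of the post-treatment scan, using the pill-count records. This would show whether the conflict ever arose. It costs one listing and leaves the completed Aim 1 analysis set unchanged.
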